8.2 Description of study procedures

Medical history

Findings from medical history (obtained at screening) and physical examination shall be given a baseline grade according to the procedure for AEs. Increases in severity of pre-existing conditions during the study will be considered AEs, with resolution occurring when the grade returns to the pre-study grade or below.

Physical examination

Physical examinations should be conducted according to the Schedule of Events. Full physical examinations should be conducted at screening/baseline, day of mapping, day of Y90 therapy and beyond, and EOT (evaluate all major organ systems, including the following categories: general, head, eyes, heart, lungs, abdomen, extremities, neurologic, and psychiatric). Other examinations may be focused, at the discretion of the Investigator, to identify changes from baseline or evaluate changes based on the patient's clinical symptoms. Weight is to be reported at each visit, height at screening/baseline visit only.

Vital signs

Vital signs (blood pressure [BP], pulse, temperature, and respiration rate) will be evaluated according to the assessment schedules. Body weight is also recorded along with vital signs.

Clinical laboratory tests

The following clinical laboratory tests will be performed (see the Schedule of Assessments)

- Hematology and Clinical Chemistry
- Coagulation parameters: Activated partial thromboplastin time and International normalised ratio to be assessed at baseline and as clinically indicated
- Pregnancy test (female subjects of childbearing potential only)
 - Urine human chorionic gonadotropin (at screening only)
 - Serum beta-human chorionic gonadotropin

Hematology Laboratory Tests

Basophils	Mean corpuscular volume
Eosinophils	Monocytes
Hematocrit	Neutrophils
Hemoglobin	Platelet count
Lymphocytes	Red blood cell count
Mean corpuscular hemoglobin	Total white cell count
Mean corpuscular hemoglobin concentration	

Clinical chemistry (serum or plasma) Laboratory Tests

Albumin	Glucose
Alkaline phosphatase	Lactate dehydrogenase
Alanine aminotransferase	Lipase
Amylase	Magnesium
Aspartate aminotransferase	Potassium
Bicarbonate	Sodium
Calcium	Total bilirubin ^a
Chloride	Total protein

Clinical chemistry (serum or plasma) Laboratory Tests

Albumin	Glucose
Creatinine	Urea or blood urea nitrogen, depending on local practice
Gamma glutamyltransferase ^b	Uric acid

^a If Total bilirubin is $\geq 2 \times \text{ULN}$ (and no evidence of Gilbert's syndrome) then fractionate into direct and indirect bilirubin

^b At baseline and as clinically indicated

9. MEASUREMENT OF EFFECT

Response and progression will be evaluated in this study using m-RECIST [42].

9.1 m-RECIST Criteria

At baseline, tumor lesions/lymph nodes will be categorized as measurable or non-measurable as described in the following subsections.

For the purposes of this study, patients should be re-evaluated for response at 1, 3 and 6 months post Y90 therapy.

Definitions

Evaluable for toxicity. All patients will be evaluable for toxicity from the time of their first treatment with *Y90 therapy*.

Evaluable for objective response. Only those patients who have measurable disease present at baseline, have received Y90 therapy, and have had their disease re-evaluated will be considered evaluable for response. These patients will have their response classified according to the definitions stated below. (Note: Patients who exhibit objective disease progression prior to the completion of study could be considered for alternate therapy after documentation of PD at 3 months.)

Disease Parameters

Measurable disease. Measurable lesions are defined as those that can be accurately measured in at least one dimension (longest diameter to be recorded) as ≥ 20 mm by chest x-ray or as ≥ 10 mm with CT scan, MRI, or calipers by clinical exam. All tumor measurements must be recorded in millimeters (or decimal fractions of centimeters).

Note: Tumor lesions that are situated in a previously irradiated area might or might not be considered measurable. *If the investigator thinks it appropriate to include them, the conditions under which such lesions should be considered must be defined in the protocol.*

Malignant lymph nodes. To be considered pathologically enlarged and measurable, a lymph node must be ≥ 15 mm in short axis when assessed by CT scan (CT scan slice thickness recommended to be no greater than 5 mm). At baseline and in follow-up, only the short axis will be measured and followed.

Non-measurable disease. All other lesions (or sites of disease), including small lesions (longest diameter <10 mm or pathological lymph nodes with ≥ 10 to <15 mm short axis), are considered non-measurable disease. Bone lesions, leptomeningeal disease, ascites, pleural/pericardial effusions, lymphangitis cutis/pulmonitis, inflammatory breast disease, and abdominal masses (not followed by CT or MRI), are considered as non-measurable.

Note: Cystic lesions that meet the criteria for radiographically defined simple cysts should not be considered as malignant lesions (neither measurable nor non-measurable) since they are, by definition, simple cysts.

‘Cystic lesions’ thought to represent cystic metastases can be considered as measurable lesions, if they meet the definition of measurability described above. However, if non-cystic lesions are present in the same patient, these are preferred for selection as target lesions.

Target lesions. All measurable lesions up to a maximum of 5 lesions per treated liver lobe will be identified as target lesions and recorded and measured at baseline. Target lesions should be selected on the basis of the size of their enhancing portion but in addition should be those that lend themselves to reproducible repeated measurements. It may be the case that, on occasion, the largest lesion does not lend itself to reproducible measurement in which circumstance the next largest lesion which can be measured reproducibly should be selected.

Non-target lesions. All other lesions (or sites of disease) including any measurable lesions over and above the 5 target lesions should be identified as **non-target lesions** and should also be recorded at baseline. Measurements of these lesions are not required, but the presence, absence, or in rare cases unequivocal progression of each should be noted throughout follow-up.

Methods for Evaluation of Measurable Disease

All measurements should be taken and recorded in metric notation using a ruler or calipers. All baseline evaluations should be performed as closely as possible to the beginning of treatment and never more than 4 weeks before the beginning of the treatment.

The same method of assessment and the same technique should be used to characterize each identified and reported lesion at baseline and during follow-up.

Multiphase Liver Mass Protocol CT and MRI: Liver mass protocol MRI is the preferred imaging modality in this study. This guideline has defined measurability of lesions on CT scan based on the assumption that CT slice thickness is 5 mm or less. If CT scans have slice thickness greater than 5 mm, the minimum size for a measurable lesion should be twice the slice thickness.

FDG PET/CT: PET/CT is not an ideal modality for evaluation HCC at baseline or after therapy.

Ultrasound: Ultrasound is not useful in assessment of lesion size and should not be used as a method of measurement. Ultrasound examinations cannot be reproduced in their entirety for independent review at a later date and, because they are operator dependent, it cannot be guaranteed that the same technique and measurements will be taken from one assessment to the next. If new lesions are identified by ultrasound in the course of the study, confirmation by CT or MRI is advised. If there is concern about radiation exposure at CT, MRI may be used instead of CT in selected instances.

Tumor markers: Tumor markers alone cannot be used to assess response. If markers are initially above the upper normal limit, they must normalize for a patient to be considered in complete clinical response.

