3. OBJECTIVES AND ENDPOINTS

OBJECTIVES	ENDPOINTS
Primary	
To compare the safety and accuracy/efficacy of low dose Y90 resin microspheres and MAA in predicting the actual dose delivered to the tumor, liver, and lung after Y90 therapy.	
 • Safety: adverse events related to Y90 radioembolization and angiography will be document by physical examination, clinical laboratory test and cross-sectional imaging. • Accuracy/Efficacy: The accuracy/efficacy of MAA as a predictor of therapeutic Y90 distribution will be compared to that of low-dose Y90.
Secondary	
 1. To Identify tumor dose response thresholds (TDRT) and tumor dose distribution in patients with HCC treated with Y90 resin microspheres. 2. To optimize low dose Y90 techniques in predicting TNR and LSF. 
 • Imaging Modified Response Criteria in Solid Tumors (m-RECIST) will be used on follow-up multiphase CT or MRI at 1, 3 and 6 months post Y90 radioembolization • Tumor dose response threshold will be determined • Imaging parameters for both Y90 SPECT and PET in both low and therapeutic dose will be optimized with the goal of recommending one of either SPECT or PET as the feasible imaging modality of choice at the conclusion of the study.

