4. STUDY DESIGN

4.1 Overall Design

This study is a single arm phase II prospective clinical trial in which patients with HCC who are deemed suitable for Y90 radioembolization will be recruited. Patients will undergo standard of care mapping study with ^{99}Tc -MAA to plan for Y90 radioembolization therapy. The additional, non-standard of care, intervention will be to do a second mapping study using low-dose Y90 (15 mCi) before the therapeutic Y90 radioembolization.

The distribution of MAA in terms of lung shunt fraction (LSF) and tumor to normal liver activity ration (TNR) will be compared to that of low-dose Y90. The treatment planning will be performed using standard of care MAA biodistribution using partition dosimetry model.

After administration of therapeutic Y90 dose, the actual dose delivered to tumor, non-tumoral liver (NTL) and lungs will be compared to the dose predicted by MAA and low-dose Y90.

The patients will be followed-up clinically and with imaging at 1, 3 and 6 months to determine tumor response, potential treatment related toxicity and to determine TDRT.

Hypothesis: Low dose Y90 microspheres as the treatment planning radiotracer will allow more accurate prediction of therapeutic Y90 liver biodistribution, which will enable us to perform prospective personalized dosimetry for every individual patient.

The results of this study will determine the safety and efficacy of using low dose Y90 as a direct surrogate for treatment planning to ensure delivering cytotoxic Y90 dose to the targeted tumor(s), while concomitantly minimizing liver and lung toxicity with more accurate prediction of therapeutic Y90 biodistribution. **Our long-term objective is to increase the likelihood of objective tumor response, prolonged progression-free survival (PFS) and overall survival (OS) in patients with HCC treated with Y90 RE.**

The study is a single-arm in study in which each patient will undergo two sets of mapping procedure before the actual Y90 therapy. One with standard of care ^{99}Tc -MAA and one with low-dose (15 mCi) Y90 microspheres. **Therefore, the additional intervention in the study is the second mapping procedure with low-dose Y90 microspheres.** Each patient will be used as their internal control to minimize selection biases. **Additional to standard of care Y90 SPECT/CT after therapy, the patient will undergo one PET/CT after low-dose Y90 and one PET/CT after Y90 therapy.**

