10.5 Safety Analyses

Adverse event data will be described and graded per the NCI CTCAE 5.0 guidelines. For each adverse event, information to be collected includes event description, time of onset, clinician assessment of severity, relationship to study product (assessed only by those with the training and

authority to make a diagnosis), and time of resolution/stabilization of the event. Regardless of relationship, all AEs will be recorded with start dates occurring any time after patient receives Y90 until 7 (for non-serious AEs) or 100 days (for SAEs) after the last day of study participation. At each study visit, the investigator will inquire about the occurrence of AE/SAEs since the last visit. Events will be followed for outcome information until resolution or stabilization.

Any medical condition that is present at the time that the participant is screened will be considered as baseline and not reported as an AE. However, if the study participant's condition deteriorates at any time during the study, it will be recorded as an AE. Changes in the severity of an AE will be documented to allow an assessment of the duration of the event at each level of severity to be performed. AEs characterized as intermittent require documentation of onset and duration of each episode.

The maximum grade for each type of toxicity will be recorded for each patient, and frequency tables will be reviewed to determine toxicity patterns. Adverse events will be summarized and described within each cohort. They will initially be reviewed regardless of attribution, but also whether they are possibly, probably, or definitely related to treatment. In addition, we will review all adverse event data that are graded as 3, 4, or 5 and classified as either "unrelated" or "unlikely to be related" to study treatment in the event of an actual relationship developing. The incidence of severe adverse events or toxicities will be described. We will assess the proportion of patients who experience grade 3 or higher non-hematologic toxicity. To assess tolerability, we will also capture the proportion of patients who go off treatment due to adverse events.

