11.5 Adverse Event and Serious Adverse Event Reporting

11.5.1 Adverse Event Reporting

From the time of treatment allocation through **90** days following cessation of treatment, all adverse events, that begin or worsen after informed consent, **must be recorded** by the investigator or designee at each examination on the Adverse Event case report forms/worksheets.

The investigator will make every attempt to follow all subjects with non-serious adverse events for outcome.

Conditions that were already present at the time of informed consent should be recorded in the Medical History page of the patient's CRF/worksheet.

Adverse events will be assessed and graded according to the Common Terminology Criteria for Adverse Events (CTCAE) version 5.0. Grade 1 to 5 will be used to characterize the severity of the Adverse Event.

If CTCAE grading does not exist for an adverse event, the severity of mild, moderate, severe, and life-threatening, death related to the AE corresponding respectively to Grades 1 - 5, will be used. Information about any deaths (related to an Adverse Event or not) will also be collected through a Death form (or EOT/SEC/Survival Information in NOVDD). The occurrence of adverse events should be sought by non-directive questioning of the patient (patient) during the screening process after signing informed consent and at each visit during the study. Adverse events also may be detected when they are volunteered by the patient (patient) during the screening process or between visits, or through physical examination, laboratory test, or other assessments. As far as possible, each adverse event should be evaluated to determine:

1. The severity grade (CTCAE Grade 1-5)
2. Its duration (Start and end dates)
3. Its relationship to the study treatment (Reasonable possibility that AE is related: No, Yes) or Its relationship to the study treatment (Reasonable possibility that AE is related: No, Yes, investigational treatment, Yes, the study treatment (non-investigational), Yes, both and/or indistinguishable)
4. Action taken with respect to study or investigational treatment (none, dose adjusted, temporarily interrupted, permanently discontinued, unknown, not applicable)
5. Whether medication or therapy was given (no concomitant medication/non-drug therapy, concomitant medication/non-drug therapy)

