For the time period beginning at treatment allocation through **90** days following cessation of treatment, or **180** days following cessation of treatment if the subject initiates new anticancer therapy, whichever is earlier, any serious adverse event, or follow up to a serious adverse event, including death due to any cause whether or not related to the study drug, must be **submitted on an SAE form** and assessed by PI in order to determine reporting criteria to regulatory authorities, IRB, DSMC, FDA or Sponsor.

All SAEs will be followed until satisfactory resolution or until the site investigator deems the event to be chronic or the adherence to be stable. Other supporting documentation of the event may be requested by the study sponsor and should be provided as soon as possible. The study sponsor will be responsible for notifying FDA of any unexpected fatal or life-threatening suspected adverse reaction as soon as possible but in no case later than 7 calendar days after the sponsor's initial receipt of the information.

All subjects with serious adverse events must be followed up for outcome.

Any additional information for the SAE including complications, progression of the initial SAE, and recurrent episodes must be reported as follow-up to the original episode **within 24 hours** of the investigator receiving the follow-up information.

An SAE occurring at a different time interval or otherwise considered completely unrelated to a previously reported one should be reported separately as a new event.

Any SAEs experienced after the reporting period described above should only be reported to FDA/IRB if the investigator suspects a causal relationship to the study treatment.

Information about all SAEs is collected and recorded on the **Serious Adverse Event Report Form**; all applicable sections of the form must be completed in order to provide a clinically thorough report. The investigator must assess and record the relationship of each SAE to each specific study treatment (if there is more than one study treatment), complete the SAE Report Form, and submit the completed form.

Each reoccurrence, complication, or progression of the original event should be reported as a follow-up to that event regardless of when it occurs. The follow-up information should describe whether the event has resolved or continues, if and how it was treated, whether the blind was broken or not, and whether the patient continued or withdrew from study participation.

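### Sections 9.1, 10.5 and 11.5 start the safety count at different points and no safety population is defined, so the low-dose Y90 mapping could fall outside the toxicity denominator

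*Combined protocol and SAP*

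**What the plan says.** Four places set a start for safety.

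- **Section 9.1, Definitions:** "All patients will be evaluable for toxicity from the time of their first treatment with" Y90 therapy.
- **Section 10.5, Safety Analyses:** "all AEs will be recorded with start dates occurring any time after patient receives Y90".
- **Section 11.5.1:** from treatment allocation, recording of "all adverse events, that begin or worsen after informed consent".
- **Section 11.5.2, for serious events:** "For the time period beginning at treatment allocation through" a stated number of days after treatment ends.

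Section 4.1 identifies what the trial adds to usual care: "the additional intervention in the study is the second mapping procedure with low-dose Y90 microspheres". Section 3 lists safety under the primary objective and includes the catheter procedures: "adverse events related to Y90 radioembolization and angiography will be document by physical examination". Section 10.1 applies no statistical consideration to safety and points to 10.5 for the detailed plan. Section 10.5 promises a proportion of patients with grade 3 or higher non-hematologic toxicity but does not say which patients form the denominator. The term safety analysis set appears only in the abbreviation list in Appendix B.

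**The concern.** The safety of low-dose Y90 mapping is half of the primary objective. The research-specific exposure is the second catheterisation, the arterial sheath kept in place between the two mapping procedures, and the 15 mCi injection. All of it happens on the Monday, before therapy. The only sentence that says who is evaluable for toxicity starts the clock at therapy on the Wednesday or Thursday.

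An analyst who takes that sentence as the safety-set definition would report toxicity for therapeutic radioembolization, which is standard care here, and leave out the procedure under study. A patient who had the low-dose injection and was then not treated would not appear at all. That patient may be the one whose mapping went badly.

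**Working it through.** The plan states no figure on this point to reproduce. The check compares the start points and measures the gap between them.

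**1. What Y90 therapy means.** Section 4.1 schedules "one PET/CT after low-dose Y90 and one PET/CT after Y90 therapy", so the two are separate events. Section 7.7 lists inability to receive Y90 therapy as a reason for withdrawal, which makes sense only for the therapeutic administration. The 9.1 clock therefore starts at the third angiography.

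**2. What each rule covers.**

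| Event or patient | 9.1 | 10.5 | 11.5.1 / 11.5.2 |
|---|---|---|---|
| First mapping angiography (MAA) | No | No | Depends on when allocation occurs |
| Sheath interval and second catheterisation before injection | No | No | Probably |
| Low-dose injection to therapy | No | Yes, if Y90 includes the low dose | Yes |
| Patient mapped but not treated | No | Yes, on the same reading | Yes |
| Therapy onward | Yes | Yes | Yes |

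Treatment allocation is not defined, and the trial has one arm. Section 6 registers patients after all entry requirements are met, yet inclusion criterion q uses planar MAA imaging. Allocation could therefore be read as falling after the first angiogram.

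**3. Length of the gap.** In section 1.3, low-dose delivery ends at 1:00 PM on Monday and the therapeutic procedure starts at 11:00 AM. Section 8.1 allows Wednesday or Thursday.

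- To Wednesday: 48 − 2 = 46 hours.
- To Thursday: 72 − 2 = 70 hours.

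Both mapping angiographies also precede the 9.1 start.

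**4. The plan's own extreme case.** Section 4.3 considers a lung shunt fraction of 100%. With the lung-dose formula in 7.1.2 and a lung mass of 1 kg:

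- 15 mCi × 0.037 = 0.555 GBq
- 0.555 × 1.0 × 50 / 1 = 27.75 Gy, which agrees with the stated 27.8 Gy.

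Section 4.3 adds that this patient would not go on to therapy. Under 9.1 the patient with the highest lung exposure from the study dose would never be evaluable for toxicity.

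**5. How often someone is mapped but not treated.** The documents give no rate, so q is an assumption. For 30 mapped patients, P(at least one) = 1 − (1 − q)^30:

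- q = 3%: 1 − 0.97^30 = 60%
- q = 5%: 1 − 0.95^30 = 79%
- q = 10%: 1 − 0.90^30 = 96%

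As an illustration, suppose 31 are mapped, 30 are treated, and the untreated patient has a grade 3 event. Under 9.1 the result is 0/30. Among all mapped patients it is 1/31 = 3.2%.

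**6. Replacement.** Section 7.6 does not replace patients who received the intervention and then left. Sections 7.7 and 10.2 do. If a mapped patient is replaced, nothing in the plan keeps that patient in the safety denominator.

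**The case against.** The strongest reply is that 9.1 does not govern. Section 10.1 names 10.5 as the safety plan, and 10.5 never uses the 9.1 term. The 15 mCi dose is Y90, so read literally 10.5 opens at Monday's injection. Section 11.5 starts at allocation, and 13.2 also records all adverse reactions. The 9.1 sentence sits among response definitions. This stands in large part. A reader might infer that toxicity is counted only from therapy and that mapping-day events go uncollected; the documents do not support that, because 10.5 and 11.5 reach earlier. But recording is not analysis. Section 10.5 states no denominator, so 9.1 is the only population rule available to whoever writes the tables.

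A second reply is that the MAA angiogram is standard care, so its events say nothing about the intervention. That is fair as to attribution. Section 3, however, puts angiography events in the primary safety objective without that limit, and with one sheath serving both mapping procedures an access-site event cannot be cleanly assigned to either. Onset dates are collected, so periods can be separated at analysis; the plan should still say that they will be.

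A reader might also try to size the untreated group from the lung shunt distribution in 10.2. A lognormal with mean 11.66 and SD 10.2 puts about 14% of patients above 20%. That is not a mapped-but-untreated rate. Sections 7.1.2 and 7.1.3 provide for treating such patients with modified activity, MAA imaging comes before the low-dose injection in the day's timetable, and both the shape and the transfer to this restricted population are assumed.

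**Conclusion.** The conflict is real. There are three kinds of start point (first Y90 therapy, receipt of Y90, treatment allocation) and no defined safety population for a primary safety objective. Applied as the denominator, 9.1 would exclude the study intervention, 46 to 70 hours of follow-up after it, and every patient mapped but not treated. Applied instead, 10.5 would still omit angiography events before the injection, and its wording does not settle whether the low dose counts.

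The conclusion rests on Y90 therapy meaning the therapeutic administration, which sections 4.1 and 7.7 support. The 60% to 96% range rests on an assumed untreated rate of 3% to 10%. The finding does not show that safety data will be lost. It shows that the plan permits different safety tables from the same data, one of which leaves out the exposure of interest.

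**What to change.** - Replace the 9.1 sentence with a named safety population: all patients who start the first mapping angiography.
- Count adverse events from first arterial access. Align 9.1, 10.5, 11.5.1 and 11.5.2 to that start, and state in 10.5 that Y90 includes the low dose.
- Tabulate events from mapping to therapy separately from events after therapy. Give the number who started mapping, received low-dose Y90 and received therapy, so that each proportion has a visible denominator.
- Reconcile 7.6 with 7.7 and 10.2 on replacement. Whichever is kept, state that patients mapped and then withdrawn or replaced stay in the safety denominator.

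The cost is wording changes and one extra table split. Sample size, treatment and the efficacy analysis are unaffected. Some patients in the population may have had only the MAA angiogram, which is why the separate counts are needed.
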